6.6. Screening visit

After the participant signs the consent, the participant will continue with screening assessments and baseline measurements. The participant's health status will be evaluated by a study clinician using a biometric assessment (blood pressure, height, weight and body mass index), vital signs (pulse rate and temperature), a screening exam, a mood assessment (Geriatric Depression Scale-15) and cognitive assessments (Clinical Dementia Rating and Mini Mental State Examination). A non-fasting plasma and urinary laboratory evaluation (complete blood count, comprehensive metabolic panel and urinalysis) will be performed and submitted to the OHSU clinical core laboratory to identify asymptomatic illnesses that could impact study results

(Table 5). A member of the study staff with venipuncture training or CTRC nursing personnel will collect approximately three teaspoons (15 mL) of venous blood by peripheral venipuncture and the participant will collect half a cup of urine (20 mL) via a clean-catch method for analysis. . An aliquot of urine (15 mL) and of blood (3 mL; spun down to plasma) will be frozen for later LC-MS analysis for the bioactive compounds of interest (see section 6.9). One aliquot of blood (5 mL) will be used to prepare PBMC for evaluation of NRF2 gene expression and/or protein levels. Blood and urine collected for safety assessments will initially be treated per standard laboratory processing methods in the CTRC laboratory and transported to OHSU Hatfield Lab Services (Hatfield Research Building) for further processing and analysis. These labs will need to be collected within two weeks of consent. Participants will be provided with a handout describing the “low plant diet” that they are to follow prior to each study visit, should they qualify for the study. The visit is expected to take 45-60 minutes. Study assessments will only be started after the subject and study partner (ARR) have signed the consent form.

A study clinician will review screening and laboratory results prior to participant enrollment. Participants will be contacted by phone and told whether they qualify for the study or not within one week of study enrollment. Participants meeting all final eligibility criteria will be invited to participate in the intervention phase of the study and will be scheduled for Study Visit 1. Any participants with abnormal health screening or laboratory evaluation will be directed to their primary care physician for treatment and excluded from the study. In the event that a participant does not qualify for the study, their data will be destroyed at the end of the study.

6.7. Documentation of ineligibility or non-participation of eligible candidates

A participant’s qualification for participation in the intervention phase of the study will be documented on the medical history case report form collected at screening and initialed by the study personnel who determined eligibility. It will be documented on this same form if an eligible participant elects not to participate. If a participant elects to drop out of the study, this will be documented on their phone follow-up script and input into their instance of REDCap.

6.8. Enrollment

Enrollment will be defined as the date of randomization. Randomization will occur once the individual agrees to participate and all screening criteria have been met. This should occur between 72 hours and two weeks following their screening visit.

6.9. Study visits 1 and 2

Visit timing: Visit 1 will occur a minimum of 72 hours following randomization and the screening visit to ensure adequate time for the low plant diet the screening laboratory results and for scheduling of appropriate facilities. Visit 2 will occur approximately 2-4 weeks following Visit 1 to allow for complete wash out of the study intervention (Figure 3).

Low phytochemical “plant” diet: Due to the nature of the bioactive compounds from *Centella asiatica*, participants will be required to adhere to a “low plant diet” designed by the Oregon Clinical and Translational Research Institute Bionutrition Department at OHSU. They will comply with this diet for 48 hours prior to each study visit, for which they will be given a handout at the screening visit. The diet is essentially limiting intake of fruits, vegetables, coffee, whole grains, chocolate and tea, which may contain compounds similar to those found in *Centella asiatica*. Participants will be provided with food conforming to this diet for the duration of each study visit including three full meals and snacks as needed. To assess for success of the diet, a small amount of the blood obtained at the screening visit will be analyzed for the presence of the bioactive compounds while the participant is following their normal diet and then compared to baseline levels at each study visit. To monitor for dietary compliance, a 48-hour diet diary will be

provided to each participant to be filled out each day and brought to each study visit. The diary will also include areas for documenting supplement and medication usage.

Sample collection: Participants will be asked to fast for 10 hours prior to each study visit, excluding water, in an attempt to standardize gastrointestinal transit time and minimize delayed absorption of the study intervention due to the presence of food. A study clinician or CTRC nursing staff member will place a peripheral intravenous catheter in the participant's arm or hand to allow for serial plasma specimen collection. Prior to administration of the *Centella asiatica* product, a baseline blood sample of one tablespoon (15 mL) will be collected through the catheter using a syringe and transferred immediately into a heparinized Vacutainer tube. The participant will be asked to consume by mouth one of the two doses of *Centella asiatica* product dissolved in 8-12 ounces of warm water, on an empty stomach in the presence of study personnel to ensure compliance. Participants will be asked not to consume food for two hours following consumption of the study intervention to allow for transition into the small intestine and absorption. If signs of hypoglycemia present, participants will be allowed to consume a high glycemic food and monitored for improvement. Serial blood samples (two or three teaspoons (10 -15 mL)/sample) will be obtained through the peripheral intravenous catheter using a syringe over a 10-hour post-administration period (15, 30, 45, 60, 90, 120, 150, 180, 240, 360, 480, and 600min) (Table 4). The 15 mL samples will be collected at 60, 120, 180, 240 and 360 mins to allow for 5 mL to be processed for PBMC isolation. Participants will collect their urine for the duration of the study visit (10 hours) to assess for excretion of *Centella asiatica* metabolites.

Tolerability and safety: We will record weight, height, body mass index, and age at baseline and blood pressure, temperature and pulse rate at baseline and ten hours post-administration at each study visit to monitor for adverse events and asymptomatic illnesses that may impact study results (Figure 3, Table 5). We will also collect serum kidney and liver function markers at each study visit (a comprehensive metabolic panel) at baseline and ten hours post-administration (Table 5). Participants will have an electrocardiogram (EKG) at the beginning of each study visit and six hours after intervention administration. Participants will be interviewed and administered a standardized multi-system adverse events questionnaire at the beginning and end of each study visit. This questionnaire has been adapted from the National University of Natural Medicine approved questionnaire (Appendix).

Table 5. Schedule of study visits and assessments.

Event	Screening	Visit 1	Visit 1 + 1 day	Visit 2	Visit 2 + 1 day	Visit 2 + 7 days
		Study visit	Phone visit	Study visit	Phone visit	Phone visit
Informed consent	•					
Vitals ⁺	•	•		•		
Health screening	•					
Cognitive assessment [#]	•					
Biometric assessment	•	•		•		
Electrocardiogram (ECG)		•		•		
Blood draw (CBC, CMP*) and urinalysis	•	• ^{V, U}		• ^{V, U}		
Low plant diet (starting 48h prior to visit)		•		•		
Single dose of intervention		•		•		
Blood collected at intervals (0-10hr) for bioavailability, antioxidant and NRF2 activation assessment	• [^]	•		•		

10-hour urine collection, baseline urinalysis		•		•		
Adverse events (AE) questionnaire		• ^Q	•	• ^Q	•	•

* Vitals include blood pressure, temperature and pulse rate; measured once at screening, and at baseline and ten hours post administration at study visits; * CBC = Complete Blood Count with differential; CMP = Comprehensive Metabolic Panel, ^ Single time point, #Mini Mental State Exam, Clinical Dementia Rating, Geriatric Depression Scale-short form, [∇]CMP only collected at baseline and ten hours post administration, ^U- urinalysis at baseline only; ECG collected at baseline and six hours post-administration; ^Q – adverse event questionnaire administered at baseline and end of visit.

Baseline measurements at each visit:

- Plasma and urinary levels of bioactive compounds (triterpenes and caffeoylquinic acids) derived from the diet.
 - Plasma and urine collected in the screening visit will be analyzed to assess for success of the low phytochemical diet
- NRF2 gene expression and/or nuclear protein levels in PBMC at baseline.
 - PBMC obtained from screening visit sample will be compared to assess possible changes due the the low phytochemical diet.
- Electrocardiogram (EKG)
- Comprehensive metabolic panel (CMP)

Evaluation of Blinding Success:

At study visit 2, after administration of CAP, the participant will be asked which of the two doses, lower (2g) or higher (4g) they thought they received at this visit. The study team member will also record their opinion on which of the 2 doses they thought was administered at this visit. This information will be used to evaluate blinding success after unblinding.

6.10. Tolerability and safety assessments

Visit 1 and 2 tolerability phone assessment: Participants will be telephoned the day following each study visit to assess for delayed adverse events and/or complications from the intravenous catheter placement using interviews and a standardized multi-system adverse events questionnaire (Figure 3, Table 5). Participants will be instructed to contact a study clinician if they experience any reactions following the phone assessment, and prior to their second study visit or one-week exit interview.

Exit interview tolerability assessment: Participants will be telephoned one week following the completion of their second study visit, or first study visit if they elect to drop out of the study, to assess for delayed adverse events and/or complications from the intravenous catheter placement using interviews and a standardized multi-system adverse events questionnaire (Figure 3, Table 5).

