4.3.2. Inclusion and exclusion criteria

Inclusion criteria: Participants must meet all of the inclusion criteria below at screening to participate in this study.

1. Age 65-85, male and female
2. Meet the National Institute of Aging – Alzheimer’s Association core clinical criteria for mild cognitive impairment or probable Alzheimer’s disease dementia with a Clinical Dementia Rating (CDR) score of 0.5-1 and MMSE score of 20-28
3. Report a history of subjective memory decline with gradual onset and slow progression over the last one year before screening; MUST be corroborated by an informant
4. On cholinesterase inhibitor therapy for Alzheimer’s disease (AD) and must be on a stable dose for at least 12 weeks prior to baseline
5. Caregiver/study partner that can accompany participant to all study visits
6. Sufficient English language skills to complete all tests
7. Sufficient vision and hearing to complete all tests
8. No known allergies to *Centella asiatica*, Maltrin-100, coconut sugar, citric acid, malic acid, caramel color or any of their derivatives
9. Willingness to discontinue all botanical dietary supplements for one week prior to and during each study visit
10. Willingness to comply with a 48-hour low plant diet for each study visit
11. Absence of significant depression symptoms (Geriatric Depression Scale-15 score of <12)
12. Body Mass Index (BMI) greater than 17 and less than 35 at screening
13. General health status that will not interfere with the ability to complete the study

Exclusion criteria: All candidates meeting any of the exclusion criteria below at baseline will be excluded from study participation.

1. Current smoking, alcohol or substance abuse according to DSM-V criteria
2. Women who are pregnant, planning to become pregnant or breastfeeding
3. Men who are actively trying to conceive a child or planning to within three months of study completion
4. Severe aversion to venipuncture
5. Abnormal laboratory evaluation indicating asymptomatic and untreated urinary tract infection
6. Cancer within the last five years, with the exception of localized prostate cancer (Gleason Grade <3) and non-metastatic skin cancers
7. Comorbid conditions such as diabetes mellitus, kidney failure, liver failure, hepatitis, blood disorders, clinical symptomatic orthostatic hypotension, and unstable or significantly symptomatic cardiovascular disease

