6.4. Phone screening

Potential participants will be screened over the phone by a member of the study team, primarily the study coordinator, prior to coming in for the in-person screening visit. A standardized

telephone script will be used and will be submitted for IRB approval. The script will ask the study participant basic questions about eligibility and provide necessary details about the study purpose, duration of visits, number of visits and major procedures. Study personnel conducting the phone screening will then ask to talk to the participant's designated study partner to discuss the study in more detail and ask detailed eligibility questions including medical history. The telephone screening will take approximately 10-15 minutes. Potential participants that meet eligibility criteria over the phone will be scheduled for a screening visit with their study partner.

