Study partner: To ensure full comprehension of all aspects of their participation as a study partner in the study, all potential study partners will be consented in the screening visit with their participant. All in-person screening visits and consenting will occur in a Clinical and Translational Research Center's outpatient room. At the in-person screening visit, a study clinician will review the single consent/HIPAA form that describes both the screening and study procedures and then will ask the study partner to describe key points in the form (e.g. purpose of study, dietary requirements, length of study) before signing. A physical copy of their consent form will be provided to each study partner and kept in the affiliated study folders to be made available as necessary to an Independent Monitoring Committee or the OHSU IRB. To ensure ongoing consent, the study partner will be called three days prior to the second study visit to ask if they wish to continue their participation in the study. This will be documented in the participant's instance of REDCap. Appropriate language will be included in the consent form to avoid coercion. We will underscore that they can decline to participate at any point in the study, even if they have signed the consent form, and it will not impact their participation in future research trials or health care.

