7. PROVISIONS TO MONITOR THE DATA TO ENSURE SUBJECT SAFETY

Adverse event (AE) monitoring will occur in “real time” using a standardized Adverse Event Monitoring Form and reviewed weekly by the principal ([name]) and clinical ([name]) investigators. This form is a ninety-one point multi-system questionnaire that assesses all organ systems (eyes/ears/nose/throat, gastrointestinal, neurological/ musculoskeletal, psychological/general, cardiopulmonary, skin, genitourinary and whole body systems). It will be completed at the screening visit in order to collect data on any/all pre-existing symptoms and their severity, and will serve as baseline data to determine attribution to the study intervention. The Adverse Event Monitoring Form will be administered in person at the beginning and end of Visits 1 and 2, via telephone the day following Visit 1 and 2, and by telephone one week after Visit 2, to assess for acute and delayed adverse events. Electrocardiograms will be performed just prior to administration of *Centella asiatica* product and six hours after intervention to monitor for adverse events. This time point has been selected based on prior pharmacokinetic literature on *Centella asiatica* triterpenes and from our murine studies which suggest that at 6 hours, the bioactive triterpenes should have reached maximum concentration and the caffeoylquinic acids are beyond their time of maximum concentration. This is also to allow for the collection of the ECG to be feasible given the frequent timing and short intervals between blood sample collection earlier in the experiment. A comprehensive metabolic panel (CMP) will be measured at baseline of each study visit and at 10 hours after CAP administration to assess for liver or kidney toxicity. This time point was selected to allow for markers of toxicity to develop if present, and for logistical reasons to allow adequate time for sample collection, processing and transfer to the OHSU Core Laboratory for analysis within the 10 hour time frame of the experiment.

Participants will be reminded and encouraged during clinic visits to contact a study clinician if a moderate or serious AE occurs. Participants will be given a telephone number they can call at any time to report potential adverse effects. All severe AEs will immediately be reported to the Independent Monitoring Committee (IMC) and the OHSU IRB by the study principal investigator.

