9.1. Data collection methods

Information will be collected from each participant and their representative by a study clinician and/or research assistant. These personnel will be blinded to the participant's dose. The procedures for obtaining research material will include a telephone screening form, a medical history form, cognitive screening questionnaires (Mini Mental State Examination and Clinical Dementia Rating), a mood-screening questionnaire (Geriatric-Depression Scale-15), a standardized adverse event questionnaire, a diet diary, electrocardiogram, urine collection and blood collection. The following will be recorded directly on the case report forms (CRFs) telephone screening form, a medical history form, cognitive screening questionnaires (Mini Mental State Examination and Clinical Dementia Rating), a mood-screening questionnaire (Geriatric-Depression Scale-15), and a standardized adverse event questionnaire. This data will then be input into the participant's instance of REDCap. Data will be collected directly from study participants specifically for research purposes. All blood collection will be performed at the CTRC. All data used for this project will be obtained only after receiving participant informed consent.

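### The three delayed adverse-event calls are directed to participants selected for memory decline, and no study-partner input is required, so delayed symptoms may be under-reported

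*Combined protocol and SAP*

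**What the plan says.** Section 6.10 sets the follow-up of delayed events. "Participants will be telephoned the day following each study visit to assess for delayed adverse events", and for the exit interview "Participants will be telephoned one week following the completion of their second study visit". Between contacts, "Participants will be instructed to contact a study clinician if they experience any reactions following the phone assessment". Section 7 adds that "Participants will be given a telephone number they can call at any time to report potential adverse effects". The study partner is not mentioned in any of these sentences. The instrument is the ninety-one point form described in section 7.

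Section 4.3.2 admits people with CDR 0.5-1 and MMSE 20-28 and requires a history of memory decline that "MUST be corroborated by an informant". It also requires a study partner able to attend every study visit.

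At phone screening (6.4) the caller asks for the "designated study partner to discuss the study in more detail and ask detailed eligibility questions including medical history". Section 9.1 says that "Information will be collected from each participant and their representative", and its list of procedures includes the adverse event questionnaire. In Appendix 1 the diet diary is completed by the participant with the partner's help; the adverse event questionnaire row names only the study team.

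**The concern.** The participants are enrolled because their memory is failing, and entry does not rest on their own account of that decline. Yet the text governing the calls can be followed to the letter by speaking to the participant alone. A symptom that has been forgotten by the time of the call is recorded as absent.

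What is at stake is the delayed part of the safety and tolerability outcome, a secondary outcome with a stated hypothesis that a single dose is safe and well tolerated (10.4). Section 2.5.4 acknowledges that there are no human safety data on concentrated water extracts at these doses. Section 8.1 expects mainly short-lived gastrointestinal complaints and mentions possible drowsiness, which are effects learned largely by asking. With eight participants, a few lost reports would change the picture.

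**Working it through.** **1. Who is named for which contact**

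| Contact | Section | Who is named |
|---|---|---|
| Phone screening, eligibility and medical history | 6.4 | Participant, then study partner |
| Call three days before visit 2 | 6.5 | Participant and legal representative; study partner separately, about the partner's own participation |
| Diet diary | Appendix 1 | Participant, helped by study partner |
| Adverse-event calls: visit 1 +1 day, visit 2 +1 day, visit 2 +7 days | 6.10, 7 | Participant |
| Reporting between contacts | 6.10, 7 | Participant |
| Data collection in general | 9.1 | Participant and representative; no call specified |

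Section 9.1 does not settle the matter. It is one sentence covering every procedure, including ECG, urine and blood. The word representative is also unclear, because 4.3.3 says the legally authorized representative may be a different person from the study partner.

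**2. Share of scheduled reporting that rests on the calls**

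Questionnaires after the first dose for someone completing both visits (6.9, 6.10, 7, Appendix 1): end of visit 1; visit 1 +1 day (call); visit 2 pre-dose; end of visit 2; visit 2 +1 day (call); visit 2 +7 days (call). That is 6, of which 3 are calls.

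The objective measures stop earlier: ECG at 6 hours, metabolic panel and vital signs at 10 hours (6.9). After the participant leaves visit 2, the two remaining calls are the only scheduled safety data. After the visit 1 +1 day call, the next questionnaire is the visit 2 pre-dose one, with visits 2-4 weeks apart.

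**3. Size**

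The plan states no adverse event rate and no reporting probability, so there is no figure to reproduce and no bias to calculate. The following only illustrates sensitivity. Let p be the true per-participant rate of a delayed event and s the probability that it is reported. Both are assumptions. With n = 8, P(at least one report) = 1 - (1 - ps)^8:

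| p | s = 1.0 | s = 0.8 | s = 0.6 | s = 0.5 |
|---|---|---|---|---|
| 10% | 57% | 49% | 39% | 34% |
| 20% | 83% | 75% | 64% | 57% |
| 30% | 94% | 89% | 80% | 73% |

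If 0 of 8 report a delayed event, the one-sided 95% upper bound on the rate of reported events is 1 - 0.05^(1/8) = 31%. Dividing by s gives a bound on the true rate of 0.312/0.8 = 39% at s = 0.8 and 0.312/0.6 = 52% at s = 0.6. A clean result on the calls would thus be weaker evidence than it looks, to a degree the documents do not determine.

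One missed person lowers a dose's incidence by 1/8 = 12.5 points, but only if that person has no other recorded event at that dose.

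**The case against.** The strongest reply is that the plan is silent and does not exclude the partner. Section 9.1 names a representative and lists the questionnaire; Appendix 1 does not say who answers it; and the Manual of Operations, which might, is not among the documents. This stands as far as it goes. A reader might infer that no partner is ever on the call, and the text does not support that. It supports only that none is required.

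A reader might also cite the call in 6.5, where "the study partner will be called three days prior to the second study visit", as informant reporting by telephone. It is not: it asks whether the partner wishes to continue. Phone screening is the one call in which the partner supplies information about the participant.

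The impairment is mild, two of the three calls come one day after dosing, and the form prompts by organ system. These points reduce the likely loss, but they do not show it to be negligible.

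The direction is probable, not certain. Under 7.1, a pre-existing symptom forgotten at baseline and mentioned later would look new and possibly attributable. Taking the form at screening (section 7) and before each dose limits this. In the comparison of doses, the same blinded people report under both. If s is equal at both doses, the observed difference is s times the true one, which dilutes it without favouring either dose.

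**Conclusion.** The point holds as a gap in how delayed symptoms are collected. Sections 6.10 and 7 direct the three calls and between-contact reporting to the participant and require nothing of the study partner, in a population selected for memory decline. Delayed, symptom-reported events may be under-reported. The exposure is 3 of 6 scheduled questionnaires after the first dose, and all scheduled safety data after visit 2. The conclusion assumes that impaired memory lowers reporting on the calls; by how much is unknown.

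Two stronger readings are tempting and not supported:

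- **That the tolerability outcome as a whole is biased toward well tolerated.** That outcome also rests on ECG, laboratory tests, vital signs, biometrics and end-of-visit questionnaires, none of which depends on the calls.
- **That the stopping guideline in 5.9 is weakened.** It counts participants who terminate because of intervention-related events. An event that leads someone to terminate would ordinarily have come to light, and for a completer two of the three calls follow the last dose. No effect on the guideline is shown.

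This is a worthwhile, inexpensive improvement, not a demonstrated bias.

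**What to change.** In 6.10, section 7 and Appendix 1, state that each adverse-event call (visit 1 +1 day, visit 2 +1 day, visit 2 +7 days) is held with both the participant and the study partner, that the form records who reported each item, and that an event counts if either reports it. Give the reporting telephone number to the partner as well. Include the partner in the visit 2 pre-dose questionnaire, which looks back over the 2-4 week interval. Amend 9.1 so that it names the same person for these contacts.

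The cost is a few extra minutes on three calls per participant and one field on the form. The partner is already consented and already telephoned for other purposes. The downside is that a partner's report of a subjective symptom may be less specific; with the source recorded, the events can be summarised with and without partner-only reports.
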